## **Appendix III: Prohibited and Precautionary Medications**

The following information may not be all-inclusive. Our understanding of drug interactions continues to grow as new information becomes available. Please refer to the most up-to-date prescribing and drug interaction information in the respective Investigator's Brochures.

For any IMPAACT 2036 participant requiring a prohibited or precautionary medication, refer to protocol Section 8.

The remainder of this document provides further information on medications considered prohibited or precautionary with concurrent use of each study drug agent. Note that Section 2 of this document contains sub-sections listing prohibited medications for specified participants.

#### **Appendix III-A: Precautionary Medications**

IMPAACT 2036 study participants will receive both CAB and RPV. During study conduct and prior to prescribing new medications, study investigators should review drug labels, exercise caution, and exert medical judgment (in regards to risk-benefit) when prescribing a medicinal product associated with an increased risk for Torsades de Pointes (TdP), including the below medications. If questions arise when prescribing drugs associated with an increased risk of TdP, please contact the IMPAACT 2036 CMC.

- Anti-arrhythmics:
  - o Amiodarone
  - Disopyramide
  - Dofetilide
  - o Dronedarone
  - Flecainide
  - Ibutilide
  - o Procainamide
  - Quinidine
  - o Sotalol
- Antipsychotics:
  - Chlorpromazine
  - o Droperidol
  - o Haloperidol
  - o Levomepromazine
  - Mesoridazine
  - o Pimozide
  - o Thioridazine
- Anti-infectives:
  - o Clarithromycin
  - o Erythromycin
  - o Roxithromycin
  - o Pentamidine
  - Sparfloxacin

*Note:* Consider alternatives for anti-infectives, such as azithromycin, which increases rilpivirine concentrations less than other macrolides

- Gastro-intestinal drugs:
  - Cisapride
  - Domperidone
- Opiate agonists:
  - o Levomethadyl
  - o Methadone
- Antimalarials:
  - Chloroquine
  - Halofantrine
- Other:
  - Arsenic trioxide
  - o Bepridil
  - o Probucol

## **Appendix III-B: Prohibited Medications**

The below section contains listings of prohibited medications for **specified participants** at **specified timepoints during study participation** and **within 7 days prior to entry (per exclusion criterion 4.2.11)**. If, for any of the below medications, the participant cannot discontinue or change to an allowable alternative, refer to protocol Section 8.5 for participant management due to prohibited medications.

#### Prohibited Medications Throughout Study Participation (Step 1, Step 2, LSFU Participants):

The following medications may not be administered at any time during study participation, including long-term safety and washout PK follow-up (LSFU) visits:

- HIV immunotherapeutic vaccines.
- Other experimental agents, antiretroviral drugs not otherwise specified in the protocol, cytotoxic chemotherapy, or radiation therapy.
- Chronic use of systemic (oral or parenteral) glucocorticoids must be avoided due to their immunosuppressive effect; however, short treatment courses with oral prednisone/prednisolone/methylprednisolone (e.g., adjunctive treatment of Pneumocystis pneumonia with 21 days of tapering prednisone) are allowed.
- While a single dose of systemic dexamethasone is permitted, more than a single dose in a treatment course may cause significant decrease in RPV plasma concentration and is prohibited. Topical, inhaled, or intranasal use of glucocorticoids are allowed.

• Systemically administered immunomodulators (such as interleukin and interferon agents). This includes topical agents with substantial systemic exposure and systemic effects. Use of topical imiquimod is permitted (see below).

#### **Prohibited Systemically Administered Immunomodulators:**

The below is a list of examples of immunomodulators prohibited in the study. Please note that the list is not exhaustive and may be updated as needed. The IoR should consider medical history of auto-immune disease and the use of potential immunomodulators not listed below. Use of other immunomodulators that directly affect immune responses will be considered in consultation with the CMC on a case by case basis.

- Calcineurin inhibitors:
  - o Cyclosporine A
  - o Pimecrolimus
  - Tacrolimus
- Fluorouracil (including topical)
- Imiquimod topical (use within 30 days prior to entry requires consultation with the CMC)
- Interferon
- mTOR kinase inhibitors:
  - Everolimus
  - o Sirolimus
- Methotrexate purine analogues:
  - o Azathioprine
  - o 6-Mercaptopurine
- Targeted immune modulators (biological response modifiers):
  - o Abatacept
  - o Adalimumab
  - Alefacept
  - Anakinra
  - o Certolizumab
  - o Efalizumab
  - o Etanercept
  - $\circ \quad Golimumab \\$
  - o Infliximab
  - Natalizumab
  - o Rituximab
  - o Tocilizumab
  - o Ustekinumab
  - Aminosalicylates:
    - Sulfasalazine
- Aminoquinoline compounds/anti-malarial drugs commonly used to treat auto-immune disorders:
  - o Hydroxychloroquine

#### **Prohibited Medications During Study Treatment (Step 1 and Step 2 Participants):**

For participants receiving any formulation (oral or injectable) of CAB and RPV, the following medications could significantly decrease levels of CAB and/or RPV due to enzyme induction and therefore must not be administered concurrently:

• Carbamazepine

- Oxcarbazepine
- Phenobarbital
- Phenytoin
- Rifabutin
- Rifampicin/Rifampin
- Rifapentine
- Systemic dexamethasone (more than a single dose)
- St. John's wort (Hypericum perforatum)

#### Additionally,

• Hepatitis C infection therapy is prohibited in conjunction with ongoing study drug treatment (oral or injectable) through Week 24.

## Additional Prohibited Medications During Oral Lead-In (Step 1 Participants) or Oral Bridging (Step 2 Participants):

In addition, participants must discontinue the following (or change to an allowable alternative) while receiving oral RPV study product as part of the Step 1 regimen of oral CAB + oral RPV:

• Proton pump inhibitors, such as esomeprazole, lansoprazole, omeprazole, pantoprazole, rabeprazole

Additional Prohibited Medications While Receiving Injectables (Step 2 Participants)

For participants receiving CAB LA and RPV LA, use of anticoagulation agents for greater than 14 days is prohibited, with the exception of the use of anticoagulation for DVT prophylaxis (e.g., postoperative DVT prophylaxis) or the use of low dose acetylsalicylic acid (325 mg). Systemic anticoagulation (including prophylaxis doses) on the day of an IM injection should be avoided.

Note: Any prohibited medications that decrease CAB or RPV concentrations should be discontinued for a minimum of 4 weeks or a minimum of three half-lives (whichever is longer), prior to the first dose and any other prohibited medications should be discontinued for a minimum of 2 weeks or a minimum of three half-lives (whichever is longer) prior to the first dose.

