#### **Summary of Rilpivirine Drug Metabolism and Pharmacokinetics (DMPK):**

RPV LA has been administered IM to healthy adults and adults living with HIV-1 at 300 mg to 1200 mg. After IM injection of RPV LA, RPV is slowly absorbed from the injection site, exhibiting flip-flop pharmacokinetics with an apparent half-life of 200 days in adults(11).

RPV is primarily metabolised, via CYP3A, and eliminated by the liver. No dose adjustment is required in patients with mild or moderate hepatic impairment (9). Oral RPV must be taken with a

meal for optimal absorption (9). Exposure to oral RPV can be affected by modulators of CYP3A4-enzyme activity and drugs that increase gastric pH. Drugs that induce CYP3A4 activity can reduce RPV exposure and should not be co-administered. Drugs that inhibit CYP3A4 activity can increase RPV exposure but do not require dose adjustments (9). Renal elimination of RPV is negligible. Therefore, no dose adjustment of RPV is required in patients with renal impairment (9).

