Once enrolled into Cohort 1, participants in each weight band will move through two steps of study participation. In Step 1 (i.e., at study entry), participants will switch from their pre-study ART regimen to daily oral formulations of CAB + RPV for at least four weeks and up to a maximum of six weeks. Participants who meet the eligibility criteria outlined in Section 4.3 and Section 4.4 based on Week 4a visit will transition to Step 2 and receive injectable CAB LA + RPV LA through Week 72. Additional information about transitioning from Step 1 to Step 2 is provided in Section 3.3. Participants who prematurely and permanently discontinue oral CAB + RPV or do not meet eligibility criteria for the injection phase will exit the study 28 days after their last oral study product dosing (See Section 6.3.3). In Step 2, participants will receive injectable CAB LA + RPV LA. Two IM injections, a single injection of CAB LA and a single injection of RPV LA, will be administered at the Week 4b (Step 2 Entry) visit, at the Week 8 visit, and then continuing every four weeks or every eight weeks thereafter, depending on the recommendation of the Week 12 interim analyses (See Section 3.2), with the last injections administered at the Week 72 visit. In both steps, participants will follow the dosing regimens outlined in Section 5.1.

Once Cohort 1 has completed accrual (defined as having enrolled either 50 evaluable participants, as described in Section 3.2, or a maximum of 70 participants overall) and the results of both interim analyses are available and acceptable, Cohort 2 will open to accrual. Cohort 2 will have a planned accrual period of six months, during which up to 20-40 children may enroll (across both Cohort 2a and Cohort 2b, described below). Participants may enroll into either Cohort 2a or 2b, with a minimum accrual target of 4 participants in each. While distribution across weight bands is desirable, there are no weight band requirements for Cohort 2. Should the overall study sample size maximum (approximately 90 children enrolled across all cohorts) not be reached within the sixmonth accrual period for Cohort 2, then Cohort 2 will close to accrual either when the six-month accrual period is completed, or upon reaching the minimum accrual target, whichever is later.

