## 5.1.3 Oral Bridging for Participants Receiving Long-Acting Injectables

In exceptional circumstances and following consultation with the CMC, sites may provide daily oral CAB + RPV as a bridging strategy for participants who will miss a scheduled injection. Oral study product may be dispensed to study staff for providing to a participant off-site or shipped from the site directly to the participant. The pharmacist should refer to the Pharmacy Guidelines and Instructions for DAIDS Clinical Trials Networks for detailed procedures regarding shipping study product. When supplying oral bridging for participants on long acting injectables (Cohort 1 and 2a, Step 2 and Cohort 2b), the site should ensure sufficient coverage for daily use until the participant can resume study product injections. The oral study product weight band dosing regimen will be assigned according to the participant's weight obtained at the most recent study visit (whether a regularly scheduled visit or an interim visit).

Participants are to ideally begin the oral bridging regimen on the same target visit date (or within the same target visit window) as that of the missed injection visit. The last dose of the short-term oral bridging regimen should be taken on the same day as and prior to resuming injectable study product. The CMC must be consulted prior to resuming study product injections. Step 2 participants may be required to have interim injection visits upon resuming the study product injections to appropriately reinitiate the dosing regimen or to realign to the original injection visit dosing schedule.

See Section 6.9 for required procedures prior to dispensing oral study products or administering study product injections. See Section 6.5 for interim injection visits.

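### Appendix III-B: the heading extends the proton-pump-inhibitor prohibition to oral bridging, but the sentence imposing it covers only the Step 1 oral regimen

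*Protocol*

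**What the plan says.** The relevant part of Protocol Appendix III-B is headed "Additional Prohibited Medications During Oral Lead-In (Step 1 Participants) or Oral Bridging (Step 2 Participants"). The instruction under it tells participants to stop the listed drugs, or switch to a permitted alternative, "while receiving oral RPV study product as part of the Step 1 regimen of oral CAB + oral RPV". The list has one entry: "Proton pump inhibitors, such as esomeprazole, lansoprazole, omeprazole, pantoprazole, rabeprazole".

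Section 3.1 places Step 1 at the start of the study: "In Step 1 (i.e., at study entry), participants will switch from their pre-study ART regimen to daily oral formulations of CAB + RPV". Section 5.1.3 describes bridging as something else: "sites may provide daily oral CAB + RPV as a bridging strategy for participants who will miss a scheduled injection". It identifies who may be bridged as follows: "When supplying oral bridging for participants on long acting injectables (Cohort 1 and 2a, Step 2 and Cohort 2b").

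The rilpivirine pharmacokinetic summary in Section 1.2.2 states that "Exposure to oral RPV can be affected by modulators of CYP3A4-enzyme activity and drugs that increase gastric pH". That statement is about oral RPV in general and is not tied to a step.

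**The concern.** The heading and the sentence beneath it give the same rule two scopes. The heading takes in children on bridging. The sentence, which is the only text that tells anyone to do anything, stops at the Step 1 regimen. Someone checking a bridged child's concomitant medications gets a different answer depending on which line is read.

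The answer has consequences. Under Section 5.7, a participant who needs a prohibited drug while on study product must have that product held or stopped for good. Section 8.4 makes reported use of a prohibited drug a reason for a temporary hold, and Section 8.5 makes a requirement for one a reason for permanent discontinuation. Whether a proton pump inhibitor taken during bridging is prohibited can thus decide whether a child's treatment is interrupted or ended.

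**Working it through.** No arithmetic applies. The check sets the passages side by side.

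**Step 1: is bridging part of the Step 1 regimen?** By Section 3.1, Step 1 is the oral phase of Cohort 1 at entry, and Cohort 2a follows the same two steps. Bridging under Section 5.1.3 is for participants already on the injectables. It uses the same two oral drugs, but in a different phase. On its ordinary meaning, "study product as part of the Step 1 regimen of oral CAB + oral RPV" does not describe bridging.

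**Step 2: who is covered, read literally?**

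- Cohort 1 or 2a in the oral lead-in: heading yes, sentence yes.
- Cohort 1 or 2a in Step 2, on oral bridging: heading yes, sentence no.
- Cohort 2b on oral bridging: the heading reaches the child only if Step 2 is read to include Cohort 2b; the sentence does not, because Cohort 2b has no oral lead-in.

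The second line is a direct conflict. The third is an uncertainty.

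**Step 3: does another line settle it?** Proton pump inhibitors are not in the precautionary list of Appendix III-A. They are also not in the Appendix III-B lists for the whole of study participation, for study treatment with any formulation, or for participants on injectables. Nothing elsewhere in Appendix III fills the gap.

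**Step 4: is this just how the appendix is written?** The neighbouring lists also carry Step labels in their headings, but their text defines scope by exposure: all of study participation, receipt of any formulation of the two drugs, or receipt of the injectables. In those lists the label does no harm. Here the text is narrower than its own heading. The introduction to Appendix III-B says that its lists apply to particular participants at particular times, so the scope wording is meant to be followed.

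**Step 5: does the rationale separate the two periods?** The gastric-pH statement in Section 1.2.2 concerns oral RPV without limit of phase. It gives no reason for treating lead-in and bridging differently, so it does not explain the narrower sentence.

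**The case against.** The best reply is that the intent is plain. Proton pump inhibitors are the only item under the heading, so excluding bridging would leave the heading's reference to it with no content. On this view the sentence carries leftover wording, or merely names a regimen that bridging also uses. That is a fair guess at the intent, but it is still a guess: the heading and the instruction disagree, and the reader has to choose.

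A second reply is that safeguards exist. Bridging is reserved for exceptional situations and needs CMC consultation beforehand (Sections 5.1.3 and 6.5). The CMC includes pharmacologists (Section 7.1.2). Concomitant medications are recorded at each visit (Section 5.7), and Appendix III warns that it may be incomplete and points to the Investigator's Brochures. This limits the number of children affected and makes divergence between sites less likely. It does not remove the conflict, because the CMC would be applying the same text.

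A third reply concerns Cohort 2b. A reader might infer that the whole cohort falls outside the rule, since Section 5.1.3 lists it separately from Step 2. The documents do not support that as a firm conclusion. The entry criteria in Sections 4.1 and 4.2 put Cohort 2b under Step 1, Section 6.4.1 has it complete a Step 1 eligibility checklist, and the list for the whole of study participation uses Step labels while plainly meaning everyone. Section 5.1.3 itself later refers to Step 2 participants when discussing the return to injections. What stands is that the coverage of Cohort 2b is unclear.

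**Conclusion.** The inconsistency is real and sits in a rule with treatment consequences, so it is more than editorial and should be corrected. It rests on two readings: that Step 1 means the oral phase at entry, as Section 3.1 says, and that the sentence rather than the heading carries the instruction.

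Its size is small and cannot be put into numbers. The documents give neither a rate of bridging nor a rate of proton-pump-inhibitor use.

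Several stronger readings are tempting and are not supported:

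- That a proton pump inhibitor is allowed during bridging. No line permits it; the sentence simply does not reach that case.
- That all 90 children are exposed to the problem. That figure is the enrolment ceiling, not a count of children bridged while taking the drug.
- That an exposure shortfall can be calculated. The lower oral RPV limit in Section 10.3.1 is 1250 ng*h/mL against an adult geometric mean of 2083 ng*h/mL (1250/2083 = 0.60), but it is a Week 2 median criterion for choosing the oral dose, not a limit for one bridged child. The documents do not say how much exposure is lost. A bridged child also has drug from earlier injections: Section 1.2.2 gives RPV LA an apparent half-life in adults of 200 days.
- That the primary PK estimand is compromised. The prohibited-medication intercurrent event in Table 11 belongs to Cohort 1 through Week 24 and depends on the clinical pharmacologist's judgement of impact.

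**What to change.** Reconcile the Appendix III-B heading, the sentence beneath it and Section 5.1.3 so that they state one scope. Define that scope by the period in which oral RPV is taken rather than by Step label, and say expressly whether bridging is covered and whether that includes Cohort 2b. Whether the prohibition should apply during bridging is a clinical decision for the sponsor; the text only needs to give one answer.

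The cost is one sentence and one heading in Appendix III-B, with a matching reference in Section 5.1.3 if wanted. No design, sample size or analysis changes.

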# Appendix VI: Study Product Preparation Requirements for the CAB DT, RPV 2.5mg tablets, and Long-Acting Injectables

This appendix provides requirements for the CAB dispersible tablets (DT), RPV 2.5mg tablets, and long-acting (LA) injectable study product preparation for both CAB and RPV. The study product regimen, administration, formulation, storage requirements, supply and other relevant information is described in protocol Section 5 Study Product. The IMPAACT 2036 MOP provides additional details and guidance regarding study product ordering, prescribing, short-term storage, and administration.

The investigational pharmacist(s) must be proficient in the preparation of injectable study products using aseptic technique under a pharmacy biological safety cabinet (BSC) Class II or better isolator. Local regulations and site institutional policies and procedures for use of personal protective equipment, such as gloves, gowns, masks, and safety glasses, must be followed.

### Suggested supplies for CAB LA and RPV LA:

- BD 5-mL syringe, Luer-Lok Tip, Reference No.: 309646, or equivalent
- BD 3-mL syringe, Luer-Lok Tip, Reorder No.: 309585, 309657, or equivalent
- Needle for aspiration: BD Precision Glide Needle, 21G 1 inch, Reference No.: 305165, or equivalent
- Needle for intramuscular injection:
  - 23G x 1.5" SurGuard Safety Hypodermic Needle CE MARKED Mfg Catalog Number: SG3-2338 (Central Supply as applicable per country)
  - BD Precision Glide Needle, 23G 1.5", Reference No.: 305194, or equivalent

Variable needle lengths (e.g., 1.5 inch, 2 inch) and/or needles with different gauge (CAB LA: 21 to 25 gauge; RPV LA: 21 to 23 gauge) are permitted if needed to accommodate individual body types. Needle size and gauge appropriate for IM injections in children should be used.

NOTE: 25G needle is not permitted for administration of RPV LA.

## Appendix VI-A: CAB 5mg Dispersible Tablet Preparation Requirements

NOTE: Instructions below must be followed by participants in Cohort 1. Cohort 2a participants who will be using CAB dispersible tablets (DT) may disperse the tablets in liquid before ingesting, as described below, or may swallow the tablets whole (the tablets should not be chewed), followed by swallowing liquid to push the medications to the stomach. See protocol Section 5.3.1 for more information.

#### Instructions for dispersing CAB 5mg DT:

Pour the amount of clean drinking water into the study provided dosing cup needed for the prescribed dose:

- 10 mg (2 tablets) = 5 mL of drinking water
- In the event of a dose modification, instructions for preparing potential alternative dosing for CAB 5 mg DT are as follows:
  - $\circ$  5 mg (1 tablet) = 5 mL of drinking water
  - $\circ$  15 mg (3 tablets) = 10 mL of drinking water
  - o 20 mg (4 tablets) = 10 mL of drinking water
  - o 25 mg (5 tablets) = Split dose: 2 tablets in 5 mL, then 3 tablets in 10 mL

Use clean drinking water only, **do not** use any other drink or food to prepare the dose.

Add the prescribed number of tablets to the water. Do not cut or crush the tablets before adding them to the water.

Swirl the dosing cup gently for a minimum of 2 minutes to disperse the tablets. The medicine will become cloudy. Take care not to spill any of the medicine.

Check that the medicine is ready. If there are any lumps of tablet remaining, swirl the cup until they are all gone.

If any medicine is spilled, throw away the rest of the prepared medicine and make a new dose.

The dose of medicine must be given within 30 minutes of preparing the dose. If it has been more than 30 minutes wash the dose away and prepare a new dose of medicine.

Make sure that the child is upright. Give all the prepared medicine to the child.

Add another 5 mL or less of drinking water to the dosing cup, swirl and give it all to the child.

Repeat if any medicine remains to make sure the child gets the full dose.

Wash the dosing cup with water. The dosing cup will need to be clean before preparing the next dose.

